The design is an 8-week randomized, double-blind, placebo-controlled trial, with an 8-week open-label extension, of Daily Essential Nutrients (DEN; Hardy Nutritionals), and a 30-, 60-, and 365-day follow-up phone call or in person-visit. The follow-up calls will also assess for safety following study completion. Parent/guardian and child ratings, using standardized measures, will evaluate adherence, side effects and AEs (Aim 1); ADHD-associated mood and irritability (Aim 2); and ADHD symptoms (Aim 3), thus allowing evaluation for clinical significance. Other domains of psychopathology will be evaluated for purposes of sample characterization and secondary analyses. The design consists of three study periods, which are individualized for each participant as they enroll:

Child RCT Protocol 2017

1. Screening and baseline. Participants will be screened by phone through a conversation with the parent/guardian for study eligibility. Those who are eligible and consent/assent to the study will receive a baseline assessment (see below for definition of eligibility and assessment).
2. An 8-week period of fully randomized, placebo-controlled, treatment.
3. An 8-week open-label extension period (OL).

Study data collection will occur in-person at baseline and at weeks 4, 8, 12, and 16 and via phone 30-60- days after end-of-open label and 365- days after enrollment. Details of data collection are outlined in Tables 1 & 2 located on the last two pages of this proposal.

Study Population

Number of subjects

Sample size power calculations are based on using power = 0.8, with a two-tailed $\alpha=0.05$, and the a priori decision to detect a medium effect size ($d \geq .5$) with a primary parent-rated measure that is a combination of CASI-5 subscale scores. Given the three sites and two treatments; a 3:2 randomization ratio, active-to-placebo; and assuming two dropouts per arm, per site, based on a previous study (Rucklidge, 2017), ($n = 12$ total), sample needed to recruit = at least 135, with at least 123 retained. To account for the 3 sites and the 3:2 randomization, a number divisible by 15 is needed, so, $n = 45$ participants per site.

In terms of feasibility, we estimate being able to recruit the required number of participants over a period of 12-18 months, given proven success in recruitment for a vitamin D supplementation trial ([name]) and established success recruiting participants in a longitudinal study on ADHD ([name]).

Inclusion Criteria

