This study will include a vulnerable population: children.

- 1) Age inclusive of and between 6 and 12 years at the time of enrollment; 2) Verbally willing to agree to swallowing a maximum of 9-12 capsules/day with food, attend all study appointments and complete questionnaires; and 3) Meet criteria for ADHD as assessed by the clinical cut-off (6+ questions scored as 2s or 3s, “often,” or “very often,” or sufficient “sometimes” responses to meet a score of 6) on the Category A: ADHD questions from on the Child & Adolescent Symptom Inventory-5 (CASI-5) with at least several symptoms present in more than 1 setting, based on the DSM-5 symptom criteria, including significant impairment in functioning socially and/or academically⁴¹; 4) Demonstrate at least one symptom of irritability or anger as assessed by a score of 2 or 3 from an “often,” or “very often” response on one question from Category B or Rz from the CASI-5; or two “sometimes” responses; 5) Be medication-free, or washout with medical supervision to be provided by the child’s pediatrician or primary care physician, reliant on the parent/guardian to work with that physician, for *at least 2 weeks* prior to in-person study assessment. 5) Willing to give blood sample at two time points: baseline, week 8; week 16 is optional.

Participants identified as having trouble swallowing pills during the phone will be asked to complete the pill swallowing program developed by Kaplan et al[48] and successfully complete this prior to being invited to come in for a lab visit. The video can be viewed at:

Child RCT Protocol 2017

<http://research4kids.ucalgary.ca/pillswallowing>. Children who continue to be unable to swallow the pills after completing the pill swallowing program will not be included in the study.

Exclusion criteria

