At the two US sites, the child participant will be paid \$10 per in-person assessment (n=5), in the form of a gift card, (see Table 1 for assessment schedule) for a total of \$50. Gift card payment will be made for each instance the child completes the questionnaires and measures associated with that assessment time point. If the child declines to answer any questions, questionnaires and measures despite reassurance or assistance including by parent and the study coordinator, or actively declines to participate at any visit, s/he will be discontinued from the study. Children will also be paid \$10 for each blood sample provided, and \$5 for each of the other biological samples they provide, for up to \$105 for each of the 3 time points. Except for blood, children will not be withdrawn from the study for not providing a biological sample (hair, saliva, stool, urine), but the samples collection will be prioritized as part of the study. Parent/guardians will be paid \$20 for traveling to the site for in-person assessments, for a total of 5 visits during the main, 16 weeks of the study (\$100), and additionally, \$10 for questionnaires completed online and over the phone at 2-month follow up, or \$20 for parents and \$10 for the child, if 2-month follow up occurs in person. One year after enrollment in the study, participant families will be contacted regarding their willingness to provide follow-up data including questionnaires and, potentially, biological samples. Parents and children will be paid for that in-person visit, or phone visit, according to the previously described schedule: \$10 for phone completion; \$20 to parent for in-person completion; \$10 to child for in-person completion; \$5 for each biological sample provided, except blood, \$10.

At the Canadian site, payment to participants is not expected or customary. As such, parents will be given \$25 gift vouchers for their participation in the qualitative part of the study (i.e. in-person interviews) and will be reimbursed for cost of travel, including parking and mileage per onsite visit. In Canada, blood and urine will not be collected due to storage limitations. Health Canada, the Canadian equivalent of the FDA, has not required collection of blood.

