Once parent/guardian has signed consent and child participant has signed assent, and following the completion of baseline questionnaires and recording of vitals, including blood pressure, pulse, height and weight, the participant will be considered to be enrolled in the study. Enrollment may be delayed until any questions that may have arisen during the baseline assessment are discussed with and answered by the study physician. Once enrolled, the participant will be randomized to a treatment, either active or placebo, and a notification of participation letter will be sent to the child's primary care physician with the parent/guardian signature on the release of information form. Parent/guardian will be given study capsules for the initial 4 weeks as noted below.

Randomization

The randomization scheme will be generated for all three sites, as a whole, by the study statistician at OHSU using REDCap, with the randomization sequence arranged in permuted blocks of size 5, in a 3 active to 2 placebo ratio. The randomization scheme will be emailed to the other two sites. Neither the participants nor the clinicians involved in the study will have access to the randomization until end of study, but access will be available to the medical oversight person at each site and Data Safety Monitoring Board members in event of emergency. A pharmacist or designated unblinded research team member at each site will prepare individual participant pill kits in advance, per the randomization scheme. The pill kits include 1-week pill caddy containing the capsules to be taken during the first week (titrated up to the full dose by Day 5), from pre-labeled and packaged bottles sent from the manufacturer. The pill caddy, together with the bottle of pills for the rest of the month will be individually labeled and put inside a white paper bag to be given to each participant. These kits will be sequentially numbered and allocated to placebo or micronutrients based on the randomization list. The pharmacy research staff at OHSU, who is unblinded, will be available 24/7

Child RCT Protocol 2017

as per on-call schedule, to break the blind for an individual subject if medically necessary. Each participating family will be given the appropriate local clinician name and contact information in the case of a side effect or question or urgent notification for any medical emergencies.

Micronutrient formula, titration and dosing

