4. **Clinician/RA and rater blinding** will be recorded to verify integrity of the blind. Clinicians and raters will be asked whether they believe the child is assigned to the placebo, active nutrient supplement, or are unsure.

Clinician- reviewed measures

Completed at baseline, at week 8 and 16:

1. **Clinical Global Impressions Scale (CGI)** The CGI is a single-item rating of the clinician's assessment of the severity of symptoms[50]. Its goal is to allow the clinician to rate the efficacy of treatment, change over time and the severity of illness. CGI-rating will be based on 1) participant self-report, 2) parent ratings, 3) observation by RA and, 4) overview by PI.

Parent/guardian-rated measures

Completed at appropriate times during trial – see Table 1 – total time: 40 minutes or less:

1. **CASI – 5:** Subscales as noted above will be used from this behavior rating scale for DSM-5-defined emotional and behavioral disorders in youths between 5 and 18 years old
2. **PROMIS measures:** The Patient-Reported Outcomes Measurement Information System (PROMIS) measures are simple self-reports developed by the U.S. Dept. Health and Human Services to be pragmatic outcome measures in clinical trials.
(<http://www.healthmeasures.net/explore-measurement-systems/promis/obtain-administer-measures>). The child's parent/guardian will complete PROMIS scales for sleep, anxiety, peer relationships, anger, and depression. There are 4 to 13 Likert-style questions in each form. The parent/guardian answers will be used to compare to the child's responses.
3. **Strengths and Difficulties Questionnaire (SDQ):** The Strengths and Difficulties Questionnaire (SDQ) is a brief behavioral screening questionnaire designed to measure positive and negative attributes, divided between 5 scales: emotional symptoms, conduct problems, hyperactivity/inattention, peer relationships, and prosocial behaviors.
4. **Temperament in Middle Childhood Questionnaire (TMCQ):** The Temperament in Middle Childhood Questionnaire (TMCQ) will be used to assess children's reaction to a number of scenarios. It is divided in 17 categories: activation control, activity level, affiliation, anger/frustration, assertiveness/dominance, attention focusing, discomfort, fantasy/openness, fear, high intensity pleasure, impulsivity, inhibitory control, low intensity pleasure, perceptual sensitivity, sadness, shyness, and soothability/falling reactivity.

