Our primary outcome measures defined *a priori*, reflecting the often co-morbid ADHD symptoms of irritable mood and aggression are the CASI-5 subscales and the clinician CGI. The changes from baseline to the end of treatment will be compared between randomized groups using repeated-measures ANCOVA, with the baseline level as the covariate. The differences between treatment groups in these measures will be summarized as the mean differences and 95% confidence intervals generated from the ANCOVA/ANOVA models. Categorical outcomes will be compared between groups using Chi-square tests and will be described using odds ratios and 95% confidence intervals. All analyses will be undertaken on an intention-to-treat (ITT) basis that includes all randomized participants analyzed according to the group to which they were randomized. For those participants not completing the 8 weeks, data from their final assessment (last observation carried forward) will be used to evaluate the change scores. Secondary analyses will be undertaken on all outcomes using the per-protocol (completers) analysis set. All tests will be two tailed and any *p* values less than 0.05 will be considered statistically significant.

Privacy, Confidentiality, and Data Security

All staff involved in the conduct and/or monitoring of this study will have completed the requisite Human Subject Protection Training for each IRB. Documentation of training will be held in locked cabinets or secure password protected computers at each site. Prior to implementation of any protocol changes, amendments will be submitted to the Institutional Review Boards for approval. The site PIs will be responsible for continuous data and safety monitoring of all participants enrolled in this study at their respective sites; discussion of any data or safety monitoring concerns will be routinely brought up as part of weekly study coordination meetings across sites. Overt identifying information will be separated from collected data and specimens.

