A Data Safety and Monitoring Board (DSMB) will be created with a representative at each site. The members will consist of at least one person who is an expert on clinical trial safety monitoring and free of any conflicts of interest with this study. DSMB participants who have agreed to be on the board include: [name] [name], at OHSU, [name], at Nationwide Children's Hospital/The Ohio State University, and [name] from the University of Lethbridge. Every six months, the DSMB will review study recruitment, subject demographics and characteristics, and any adverse events (AEs) and safety differences that emerge between the randomized arms, including looking for differences by site. We anticipate the DSMB will meet via Skype or teleconference. To facilitate this review, the PIs will provide the DSMB with the data related to safety and efficacy. If the DSMB determines that there are significant and/or serious emergent risks within the study for any reason, the DSMB could make a recommendation to the PIs and IRBs that the study be closed for accrual of participants until a more detailed review can be conducted.

Risk and Benefits

As Co-PIs, the overseeing the risk management of the project will be handled by [name], [name], and [name], in consultation with site-specific study physicians including [name] at OHSU, [name] at Ohio State, and [name] for the University of Calgary. The Co-PIs have been and will be involved on all aspects of the project, and will, therefore, monitor for any foreseeable risks.

Risk/benefit analysis

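### The primary ANCOVA adjusts for baseline only; adding site as a three-level fixed factor is a cheap improvement, with a worst-case cost of about 0.6 power point

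*Combined protocol and SAP*

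**What the plan says.** The Data Analysis section compares changes from baseline between arms by "repeated-measures ANCOVA, with the baseline level as the covariate". Baseline is the only covariate named, and no text available to us puts site in an efficacy model.

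Site does shape the design. Number of subjects reads "Given the three sites and two treatments; a 3:2 randomization ratio, active-to-placebo; and assuming two dropouts per arm, per site", and then "To account for the 3 sites and the 3:2 randomization, a number divisible by 15 is needed", giving 45 per site and 135 in total.

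The Randomization section has one scheme generated centrally to cover the three sites together, "with the randomization sequence arranged in permuted blocks of size 5, in a 3 active to 2 placebo ratio". It does not say whether the blocks run separately within each site.

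Data Analysis names the CASI-5 subscales and the CGI as primary outcomes. Under Clinician-reviewed measures, the CGI draws partly on what the research assistant observes and on review by the PI. Its timing is "Completed at baseline, at week 8 and 16", so it has one post-baseline value in the randomised phase.

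**The concern.** When a trial is planned around a few sites and a primary outcome is partly rated by local staff, site is a natural term for the primary model. What leaving it out does depends on how allocation was arranged.

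- **Blocks within site.** The arms are balanced at each site, so between-site differences do not enter the treatment contrast. They do stay in the residual variance of a model without site. The reported standard error is then too large and the test somewhat conservative.
- **One list shared across sites.** The arms differ by chance within sites. The baseline-only standard error is right on average, but the estimate carries some avoidable between-site noise.

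At stake are the width of the confidence interval and a few points of power at most.

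**Working it through.** **Inputs.** From the protocol: N = 135, split 3:2 as 81:54; three sites of 45; blocks of five; two-sided alpha 0.05; d = 0.5; 123 retained. Assumed, because the documents give no between-site variance: site explains a share f = 0, 2, 5 or 10% of the variance left after baseline adjustment.

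**1. The plan's own figure.** Placebo n = (1 + 1/1.5) x ((1.960 + 0.842)/0.5)^2 = 52.3, rounded up to 53. Active n = 1.5 x 53 = 79.5, rounded up to 80. The total of 133 agrees with the planned 135. At 81:54, d x sqrt(81 x 54/135) = 0.5 x 5.692 = 2.846. Noncentral t on 132 df gives power 0.807.

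**2. Degrees of freedom alone.** Moving from 132 to 130 df takes power from 0.80657 to 0.80648, about 0.01 point.

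**3. Blocks within site.** 45 is nine blocks of five. The true SD of the estimate is sqrt(1 - f) times the standard error reported without site. So alpha = 2(1 - Phi(1.96/sqrt(1 - f))), and with site the noncentrality becomes 2.846/sqrt(1 - f).

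| f | alpha without site | power without site | power with site | gain (points) |
|---|---|---|---|---|
| 0% | 0.050 | 0.807 | 0.806 | 0.0 |
| 2% | 0.048 | 0.809 | 0.814 | 0.5 |
| 5% | 0.044 | 0.813 | 0.826 | 1.3 |
| 10% | 0.039 | 0.819 | 0.846 | 2.7 |

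The standard error without site is too large by 1/sqrt(0.95) - 1 = 2.6% at f = 5% and by 1/sqrt(0.90) - 1 = 5.4% at f = 10% (simulated: 2.6% and 5.0%).

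**4. One shared list.** Over 40,000 simulated lists, the number on active treatment at a site had an SD of about 2.7 (95% range 22 to 32). Adjusting for site then keeps 0.985 of the information on treatment. With site, the noncentrality is 2.846 x sqrt(0.985/(1 - f)). Break-even is where 1 - f = 0.985, so f = 1.5%.

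| f | power without site | power with site | change (points) |
|---|---|---|---|
| 0% | 0.807 | 0.801 | -0.6 |
| 2% | 0.807 | 0.808 | +0.2 |
| 5% | 0.807 | 0.820 | +1.4 |
| 10% | 0.807 | 0.840 | +3.4 |

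Changes are taken before rounding. Alpha without site stays at 0.049 to 0.051. Simulation of 60,000 trials per cell agrees with both tables to within about 0.6 point of power and 0.002 of alpha. The mean estimate under no effect was within 0.002 of zero throughout.

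**5. A stable site effect.** If sites differ equally at baseline and week 8 (baseline correlation 0.5, assumed), raw site shares of 5 / 10 / 15% shrink to 1.6 / 3.2 / 4.8% after baseline adjustment. Adding site then gains 0.4 / 0.9 / 1.3 points with blocks within site, and 0.1 / 0.6 / 1.4 with a shared list.

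**6. Sensitivity.** The tables take d = 0.5 in residual SDs. If it is in raw SDs with baseline correlation 0.5, power starts near 0.90 and the changes shrink to 0.0 / 0.3 / 0.8 / 1.5 (within site) and -0.4 / +0.1 / +1.0 / +2.3 (shared list). With 123 analysed, on the residual-SD scale, they are 0.0 / 0.6 / 1.5 / 3.0 and -0.6 / +0.2 / +1.5 / +3.6.

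**7. Repeated measures.** For the CGI, the model in the randomised phase reduces to a week-8 ANCOVA. For the CASI-5, a model with visit-specific arm, baseline and site terms gave the same week-8 estimate and standard error as the week-8 ANCOVA on one complete simulated data set.

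**The case against.** A baseline-only ANCOVA is a valid analysis, and adjusting for site is a convention rather than a requirement. Every gain above rests on an assumed site share. Where site effects are stable, which is likelier for a parent-rated scale, baseline does most of the work and little is left to gain. With a shared list and a site share below about 1.5%, adjustment loses a little power. All of this stands, and it is why the point is only a cheap improvement.

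The evidence on allocation is also mixed. Making N divisible by 15 points towards blocks within site; generating one scheme for the three sites together points towards a shared list. The text under Cross Site Coordination was not available and could not be checked, so the absence of a site term is established only for the text we have.

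A reader might infer more than the documents support:

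- **That leaving site out biases the estimate or inflates type I error.** It does neither under either arrangement.
- **That naming site now prevents a choice between two p values after unblinding.** Data Analysis already fixes one model; adding site later would be a departure from it.
- **That two degrees of freedom are the whole cost.** They cost about 0.01 point. The possible 0.6-point loss comes almost entirely from chance arm-by-site imbalance under a shared list.
- **That other site differences show a site effect on outcome.** Inclusion Criteria has "Willing to give blood sample at two time points: baseline, week 8; week 16 is optional", while Setting and Recruitment methods has "In Canada, blood and urine will not be collected due to storage limitations"; nothing links this to CASI-5 or CGI scores. The monitoring board looks at "safety differences that emerge between the randomized arms, including looking for differences by site", which concerns safety. The locally informed CGI is the relevant evidence, and it shows only that a site effect is plausible.

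**Conclusion.** The point holds as a low-cost improvement in calibration and precision. With blocks within site, a site term corrects a standard error that is about 2.6% too large at an assumed 5% share and about 5% too large at 10%, and adds about 1.3 or 2.7 power points. With a shared list, the effect runs from about -0.6 point (site explains nothing) to about +3.4 (10% share). For a stable site effect, expect about 0 to 1.4 points. These figures rest on the assumed shares, equal site sizes and d = 0.5 in residual SDs. The downside is about 0.6 point under either arrangement, so the change is worth making without first settling how the blocks were laid out.

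**What to change.** In Data Analysis, name site (three levels) as a fixed factor alongside the baseline level in the primary ANCOVA or repeated-measures model. Leave a site-by-treatment term out of the primary model. The chi-square comparisons need no change.

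The cost is one phrase in the plan and two degrees of freedom, with no extra patients or procedures. If site turns out to explain nothing, power changes by about 0 points (blocks within site) to -0.6 point (shared list).

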ClinicalTrials.gov Document Upload

DOCUMENT DATE (IRB APPROVAL):

23-Feb-2021

NCT NUMBER:

NCT03252522

OFFICIAL STUDY TITLE:

Micronutrients for ADHD in Youth:
The "MADDY" study

INVESTIGATOR NAME:

[name]

ORGANIZATION:

Oregon Health & Science University

Child RCT Protocol 2017

**Protocol for
Micronutrients for ADHD in Youth:
The “MADDY” study
at
Oregon Health & Science University
The Ohio State University/Nationwide Children’s Hospital
University of Lethbridge**

Child RCT Protocol 2017

Aims and Objectives

Aim 1: Replicate acceptability/tolerability of a multi-ingredient micronutrient product for children with ADHD [1].

Hypothesis 1: Consumption of 9-12 capsules, in 3 divided doses daily, of a product containing a blend of vitamins, minerals, amino acids and antioxidants (see Appendix A for ingredients), will be achieved at >80% success, as measured by self-report adherence and pill counts and with no or transient side effects (e.g. nausea, loose stool); and no directly attributable serious adverse events (AEs) (see definition of AE in the section on page 21) recorded via the Pediatric Adverse Events Rating Scale (PAERS).

Aim 2: Determine the prevalence, severity, and effect size for symptoms of irritability and negative mood, which are often associated with ADHD.

Hypothesis 2: Treatment will improve mood, irritability and aggression by a medium effect ($d \geq .50$) [2] as measured by the parent-rated Child & Adolescent Symptom Inventory – 5 (CASI-5), Categories B, C, CD, K, L, Rz, Q, and the child-rated Patient Reported Outcomes Measurement Information System (PROMIS) measures: Depression, Anger, Anxiety, and Peer Relations.

Aim 3: Estimate true effect sizes on ADHD symptoms in this age group, to inform a larger trial.

Hypothesis 3: The micronutrients will reduce participants' ADHD symptoms of inattention and/or hyperactivity/impulsivity, as measured by the parent-rated CASI-5, Question Category A, and the Clinician-rated Clinical Global Impression (CGI) by a medium effect ($d \geq .50$) compared to the placebo [1].

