5. **Food Frequency Questionnaire (FFQ):** The children's usual dietary intake captured over 90 days, will be assessed using a standardized, validated VioScreen FFQ, which includes 1,200 food images that users may select, based on branching logic that tracks their choices in food families.
6. **Food Insecurity Measure:** A brief measure asking to what degree the family has experienced food insecurity in the past 12 months, asked at baseline and week 8.

Child RCT Protocol 2017

7. **Parent Target Problems:** (PTP): At baseline, parents will be asked to nominate the child's biggest problem. If the parent cannot select just one, two may be named. The research assistant and parent discuss the named problem and the RA asks questions about the frequency, duration and interference level of the problem. The example field allows the parent to construct a brief narrative of the behavior and its impact on family life. The target symptoms are reviewed and the narratives revised at subsequent visits. A panel of four judges, blind to treatment condition, will independently review the narratives to rate change from baseline on a 9-point scale: 1, normal; 2, markedly improved; 3, definitely improved; 4, equivocally improved; 5, no change; 6, possibly worse; 7, definitely worse; 8, markedly worse; 9, disastrously worse. The mean of the four raters will be compared with primary and key secondary ratings from the original study.
8. **Concomitant treatment measure** will ask parents about any current treatments received (behavioral or physical), for what condition, when started and stopped, and details on dosing or frequency. This measure will be repeated at each in-person visit.
9. **Parent/guardian assessment of the blind** will be reviewed by recording a direct query of whether the parent/guardian believes the child is taking the placebo or the active product, to monitor integrity of the blind.
10. **Treatment acceptability rating** – upon study completion, the parent/guardian will be asked how participating in the study went, any suggestions they have to improve the study, and whether they would recommend the trial to others with symptoms.
11. **Treatment Review** – at 30-, 60- and 365-days post-study, parent/guardian will be asked whether his or her child is still taking the micronutrients and if yes, dosage information. Also parent/guardian will be asked about any other treatments used or obtained in the time period since last interviewed.

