3. **Child Target Problem-** At baseline, child will be asked to nominate his or her biggest problem or symptom. If the child cannot select just one, two may be named. The research assistant and child discuss the named problem and the RA asks questions about the frequency, duration and interference level of the problem. The example field allows for the construction of a brief narrative of the behavior and its impact on family life. The target symptoms are reviewed and the narratives revised at subsequent visits. A panel of four judges, blind to treatment condition, will independently review the narratives to rate change from baseline on a 9-point scale: 1, normal; 2, markedly improved; 3, definitely improved; 4, equivocally improved; 5, no change; 6, possibly worse; 7, definitely worse; 8, markedly worse; 9, disastrously worse. The mean of the four raters will be compared with primary and key secondary ratings from the original study.
4. **Treatment Acceptability**– upon study completion, the child participant will be asked for their opinion on participation and any suggestions they have to improve the study, and whether they would recommend the trial to others with symptoms.

In person at the end of the RCT

5. **Child assessment of the blind** will be captured by asking the youth whether they believe they are taking the placebo or real product.

Teacher or Other Adult-rated measures

Completed at baseline and 8 week RCT, 16-week end-of-study – time: 10 minutes:

1. **CASI-5** selected subscales (3 eligibility subscales and peer relationships) will used at baseline and to monitor the effectiveness of the child’s response to intervention at two other time points.

Data and Specimens

Blood, hair, saliva, urine, and feces collection

Collected at baseline, 8 weeks and week 16 (end-of-study) – time: 5-10 minutes

Blood collection

Per FDA requirements, participants will be **required** to provide blood samples at each in-person visit. These samples will be used for safety measures and for research purposes. Analysis will include CBC, TSH, iron, a number of supplemented nutrients including B vitamins and Vit D, and

Child RCT Protocol 2017

blood for future analysis of targeted and untargeted metabolomics and IL-6 and TNF-a. Total blood collection will be approximately 18ml, or 3 teaspoons. See “Blood Sample Collection Info for OHSU” chart included in IRB submission, for details.

Hair Collection

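### The blanket p<0.05 rule covers every non-primary clinical scale with no adjustment, testing order or exploratory label, which leaves a material, though not likely, risk of a false secondary claim

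*Combined protocol and SAP*

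**What the plan says.** Data Analysis names the primary outcomes as the CASI-5 subscales and the clinician CGI. It plans an intention-to-treat comparison and repeats all outcomes in completers. It then ends: "All tests will be two tailed and any *p* values less than 0.05 will be considered statistically significant". The sentence is not restricted to the primary outcomes.

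Clinical scales outside that primary list, all scheduled at week 8 in Table 1, are:

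- **Child PROMIS.** Hypothesis 2 (Aims and Objectives) claims a medium effect, d of at least 0.50, on parent CASI-5 categories and on "the child-rated Patient Reported Outcomes Measurement Information System (PROMIS) measures: Depression, Anger, Anxiety, and Peer Relations". It does not say how many scales must succeed. Child-rated measures adds a fifth scale, sleep.
- **SDQ.** Parent-rated, "divided between 5 scales: emotional symptoms, conduct problems, hyperactivity/inattention, peer relationships, and prosocial behaviors".
- **Parent PROMIS.** "The child's parent/guardian will complete PROMIS scales for sleep, anxiety, peer relationships, anger, and depression". The same item says these answers serve for comparison with the child's.
- **Teacher CASI-5.** "selected subscales (3 eligibility subscales and peer relationships) will used at baseline and to monitor the effectiveness" of the child's response.
- **Parent and child target problems.** Rated for change by a blinded panel: "The mean of the four raters will be compared with primary and key secondary ratings from the original study".

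The target-problem items are the only place where a key secondary tier is mentioned, and the text does not say which ratings belong to it. Design Overview assigns other psychopathology domains to sample characterisation and secondary analyses. Exploratory wording is attached only to the stool and other biological samples (Stool sample collection; Sharing of Results).

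**The concern.** A plan that names primary outcomes normally says what status the remaining comparisons have. Here the only rule gives an isolated SDQ, child or teacher result at p = 0.04 the same standing as a primary result, even when the primary analysis is null. Parent, child and teacher instruments cover overlapping domains such as anger, anxiety and peer relations, so one supposed benefit has several chances to appear. Aim 3 says that the trial is meant to inform a larger one, and a chance secondary finding could misdirect that trial's choice of endpoint.

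**Working it through.** **The plan's own figures.** No family-wise error rate is stated, so there is none to reproduce. The stated design values are a two-tailed alpha of 0.05, "Sample size power calculations are based on using power = 0.8", and an "a priori decision to detect a medium effect size" (d of at least 0.5) on one parent-rated primary measure. They imply 0.05 for one test, or 0.025 counting only a false result that favours the product.

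**Number of tests (k), week 8 only.**

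- Hypothesis 2 child PROMIS: k = 4.
- Lower count for the wider set: 5 child PROMIS + 5 SDQ = 10.
- Upper count, if every other scale is also compared between arms: 10 + 5 parent PROMIS + 4 teacher CASI-5 + 2 target problems = 21.

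Parent CASI-5 subscales and the CGI are left out as primary. Week-4 data and per-protocol repeats are not counted; including them could only raise the rates.

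**Formula.** With no treatment effect, the k test statistics are taken as standard normal with equal correlation ρ, and c = 1.96.

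- Independent tests, either direction: 1 − 0.95^k. Favouring the product: 1 − 0.975^k.
- Correlated tests, either direction: 1 − ∫ φ(u) [Φ((c − √ρ·u)/√(1−ρ)) − Φ((−c − √ρ·u)/√(1−ρ))]^k du. For results favouring the product, drop the second Φ term.

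Independent case, either direction:

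- k = 4: 1 − 0.95^4 = 0.185
- k = 10: 1 − 0.95^10 = 0.401
- k = 21: 1 − 0.95^21 = 0.659

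| Scales tested | Direction | ρ = 0 | ρ = 0.5 | ρ = 0.8 |
|---|---|---|---|---|
| 4 | either | 0.185 | 0.156 | 0.114 |
| 4 | favours product | 0.096 | 0.078 | 0.057 |
| 10 | either | 0.401 | 0.287 | 0.173 |
| 10 | favours product | 0.224 | 0.144 | 0.086 |
| 21 | either | 0.659 | 0.429 | 0.228 |
| 21 | favours product | 0.412 | 0.216 | 0.114 |

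At ρ = 0.5 the four Hypothesis 2 scales alone run at about three times the nominal level (0.156/0.05 = 3.1).

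**Cost of adjusting.** Take 123 retained at 3:2, which is 73.8 and 49.2 per arm, with no gain assumed from baseline adjustment. The standard error of d is √(1/73.8 + 1/49.2) = 0.184, and 0.5/0.184 = 2.717.

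- Power at d = 0.5 and alpha 0.05: Φ(2.717 − 1.960) = 0.775.
- At the first Holm step for four tests, alpha 0.05/4 = 0.0125: Φ(2.717 − 2.498) = 0.587.

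Power for a single scale under Holm lies between these two values.

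**The case against.** **Hypothesis 2 is framed as an effect size, not a p-value.** This is correct. With the standard error above, p<0.05 needs an observed d of only 1.96 × 0.184 = 0.36. If an observed d of 0.50 were the criterion, a false favourable result on at least one of the four scales would have probability about 0.013 (independent) or 0.012 (ρ = 0.5). A reader might infer that one p<0.05 on a child scale confirms Hypothesis 2, but the protocol does not say so. The point that remains is narrower: the plan would still call that result significant.

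**The number of tests is not fixed by the documents.** This also stands. The stated use of parent PROMIS is comparison with the child's answers, and the target-problem ratings are to be compared with other ratings. Data Analysis does not say whether its CASI-5 subscales are parent-rated only; the parent qualifier comes from Number of subjects. Hence the range of 10 to 21.

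**Tiers are not wholly absent.** Primary outcomes are named, the per-protocol work is called secondary, and Design Overview speaks of secondary analyses. None of these limits the closing rule. The passing mention of key secondary ratings is weak evidence either way, since it only describes what the panel's scores are compared with.

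**Conclusion.** The point holds as a material risk. The rule is stated and applies to all tests, and nothing in the text available for this check (parts of the recruitment and cross-site coordination sections were not) adjusts, orders or labels as exploratory the non-primary clinical scales.

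The four Hypothesis 2 scales carry an 11-19% chance of a false significant result, 6-10% in favour of the product. The wider set carries 17-66%, 9-41% in favour of the product. These figures assume no true effect on any scale, one time point, equal correlation of 0 to 0.8 and, for the wider set, 10 to 21 tests.

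A reader might infer that a false secondary benefit is likely. The figures do not support that: in the product's favour the chance stays below one half even for 21 independent tests, and for the four named scales it is at most about one in ten. The primary analysis is not affected by this point.

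**What to change.** Replace the closing sentence of Data Analysis with wording to this effect:

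1. The two-sided 0.05 rule decides the primary analysis only. Number of subjects (a combination of CASI-5 subscale scores) and Data Analysis (CASI-5 subscales and CGI) must first be reconciled on what that analysis is.
2. All non-primary clinical scales and all per-protocol repeats are exploratory or supportive. Report mean differences, standardised effects set against the 0.50 benchmark, and 95% confidence intervals, without describing any result as statistically significant.
3. Optional: if the sponsor wants a confirmatory claim on the child PROMIS scales, prespecify all four named in Hypothesis 2 as one family with a Holm adjustment.

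The change costs a few sentences and needs no new data or participants. The downside is that an isolated secondary p<0.05 can no longer be called significant. If option 3 is taken, power for one scale at d = 0.5 falls from about 78% to as little as 59%, when that scale must pass at the first Holm step.
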